6.3.1.2 General Exclusion Criteria

1. Any surgery requiring general anesthesia or discontinuation of aspirin and/or an ADP antagonist is planned within 12 months after the procedure.
2. Subject has known hypersensitivity or contraindication to device material and its degradants (everolimus, poly (L-lactide), poly (DL-lactide), lactide, lactic acid) and cobalt, chromium, nickel, platinum, tungsten, acrylic and fluoro polymers that cannot be adequately pre-medicated. Subject has a known contrast sensitivity that cannot be adequately pre-medicated.
3. Subject has known allergic reaction, hypersensitivity or contraindication to aspirin; or to clopidogrel and prasugrel and ticagrelor; or to heparin and bivalirudin, and therefore cannot be adequately treated with study medications.
4. Subject had an acute myocardial infarction (AMI: STEMI or NSTEMI) within 72 hours of the index procedure and both CK and CK-MB have not returned to within normal limits at the time of index procedure; or subject with stable angina or silent ischemia has CK-MB that is greater than normal limits at the time of the index procedure.
5. Subject is currently experiencing clinical symptoms consistent with new onset AMI (STEMI or NSTEMI), such as nitrate-unresponsive prolonged chest pain with ischemic ECG changes.
6. Subject has a cardiac arrhythmia as identified at the time of screening for which at least one of the following criteria is met:²⁸
 - a. Subject requires coumadin or any other agent for chronic oral anticoagulation
 - b. Subject is likely to become hemodynamically unstable due to their arrhythmia
 - c. Subject has poor survival prognosis due to their arrhythmia
7. Subject has a left ventricular ejection fraction (LVEF) < 30% assessed by any quantitative method, including but not limited to echocardiography, MRI, Multiple-Gated Acquisition (MUGA) scan, contrast left ventriculography, PET scan, etc. LVEF may be obtained within 6 months prior to the procedure for subjects with stable CAD. For subjects presenting with ACS, LVEF must be assessed during the index hospitalization (which may include during the index procedure by contrast left ventriculography) but prior to randomization in order to confirm the subject's eligibility.

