7.2 Pre-Procedure

7.2.1 Pre-Procedure Laboratory Assessment

The following laboratory assessments need to be obtained prior to the index procedure or at the time of the index procedure depending on the assessment and condition of the subject.

Table 7.1 Baseline Laboratory Assessment

Within 21 days prior to procedure [†]	Within 7 days prior to procedure	Within 48 hours prior to procedure [€]

• Platelet and White Blood Count• Hemoglobin• Serum Creatinine• HbA1c[‡]• Estimated GFR*	
• Pregnancy test (if applicable)	
• 12-lead ECG (within 24 hours preferred)• Creatine kinase (CK)• Creatine kinase myocardial-band isoenzyme (CK-MB)

[†]The 21 day labs must be known prior to index procedure.

[‡] HbA1c is to be collected in diabetic subjects only, and its result is not needed prior to the index procedure.

[€]Within 24 hours must be done in cases in which there is evidence of acute or recent (<7 days) myocardial infarction (MI) or unstable angina; in these cases CK and CK-MB must be < ULN prior to the index procedure. For stable angina or silent ischemia, CK and CK-MB < ULN within 48 hours prior to index is acceptable. For stable angina subjects, if CK is > ULN but CK-MB is < ULN, with no signs of MI or unstable angina, the patient maybe enrolled. If the subject does not have a known diagnosis of MI or unstable angina within 96 hours prior to the index procedure, assessment of cardiac enzymes may be obtained from arterial blood drawn after the start of the index procedure but prior to device implantation. However, if CK-MB comes back elevated a protocol deviation will be issued.

* Glomerular Filtration Rate

Both CK and CK-MB must be measured pre-procedure and used to assess subject's eligibility criteria.

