
Any one of the following criteria meets the diagnosis for prior MI:
 
• Pathological Q waves with or without symptoms in the absence of non-ischaemic causes.• Imaging evidence of a region of loss of viable myocardium that is thinned and fails to contract, in the absence of a non-ischaemic cause.• Pathological findings of a prior MI.

Modified World Health Organization (WHO) MI Definition. As a secondary analysis, MI will be adjudicated according to the modified WHO MI definition.

- **Q wave MI**

Development of new, pathological Q wave on the ECG

- **Non-Q wave MI**

- Elevation of CK levels to \geq **two** times the upper limit of normal (ULN) with elevated CK-MB in the absence of new pathological Q waves
- Non-Q wave MI definition will be used for both peri-procedural MI definition (\leq 48 hours post-procedure) and spontaneous ($>$ 48 hours post-procedure).

REVASCULARIZATION (Per ARC Circulation 2007; 115: 2344-2351)

Target Lesion Revascularization (TLR)

TLR is defined as any repeat percutaneous intervention of the target lesion or bypass surgery of the target vessel performed for restenosis or other complication of the target lesion. All TLR should be classified prospectively as ischemia driven or not ischemia driven by the investigator prior to repeat angiography. An independent angiographic core laboratory should verify that the severity of percent diameter stenosis meets requirements for clinical indication and will overrule in cases where investigator reports are not in agreement. The target lesion is defined as the treated segment from 5 mm proximal to the stent and to 5 mm distal to the stent.

Target Vessel Revascularization (TVR)

TVR is defined as any repeat percutaneous intervention or surgical bypass of any segment of the target vessel. The target vessel is defined as the entire major coronary vessel proximal and distal to the target lesion which includes upstream and downstream branches and the target lesion itself. The above two definitions will be used in this protocol.

The above two definitions will be used for CEC adjudication.

Non Target Lesion Revascularization (Non-TLR)

Any revascularization in the target vessel for a lesion other than the target lesion is considered a non-TLR.

Non Target Vessel Revascularization (Non-TVR)

Revascularization of the vessel identified and treated as the non-target vessel at the time of the index procedure.

Non-Treated Vessel

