
Inclusion Criteria
	
General Inclusion Criteria
 
 1. Subject must be at least 18 years of age. 2. Subject or a legally authorized representative must provide written Informed Consent prior to any study related procedure, per site requirements. 3. Subject must have evidence of myocardial ischemia (e.g., silent ischemia, stable or unstable angina, non-ST-segment elevation MI (NSTEMI), OR recent ST-segment elevation MI (STEMI). Patients with stable coronary syndromes can be enrolled any time after symptom onset if eligibility criteria are otherwise

	
met. Patients with acute coronary syndrome can be enrolled under the following conditions:
 
a. Unstable angina or NSTEMI within 2 weeks of the index procedure.b. STEMI > 72 hours ≤ 2 weeks prior to the index procedure. 
Note: Subjects with UA or NSTEMI or STEMI occurring > 2 weeks of the index procedure can be included in the trial but should be categorized based on their current angina class.
 
4. Subjects must be suitable for PCI. Subjects with stable angina or silent ischemia and < 70% diameter stenosis must have objective signs of ischemia as determined by one of the following: abnormal stress echocardiogram, nuclear scan, ECG, PET, MRI, and/or fractional flow reserve (FFR).
 
(Note: subject with silent ischemia must have a prior history of typical angina, angina-equivalent symptoms, or atypical angina within the past year to be included in the trial.)
 
5. Subject must be an acceptable candidate for coronary artery bypass graft (CABG) surgery.
 
6. Female subject of childbearing potential who does not plan pregnancy for up to 1 year following the index procedure. For a female subject of childbearing potential a pregnancy test must be performed with negative results known within 7 days prior to the index procedure per site standard.
 
7. Female subject is not breast-feeding at the time of the screening visit and will not be breast-feeding for at least 1 year following the index procedure.
 
8. Subject agrees to not participate in any other investigational or invasive clinical study for a period of 5 years following the index procedure.⁴⁰
 
Angiographic Inclusion Criteria
 
Treatment of up to three de novo lesions in a maximum of two epicardial vessels, with a maximum of two lesions per epicardial

--	---

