	
1. Any surgery requiring general anesthesia or discontinuation of aspirin and/or a P2Y12 receptor inhibitor is planned within 12 months after the procedure.2. Subject has known hypersensitivity or contraindication to device material and its degradants (everolimus, poly (L-lactide), poly (DL-lactide), lactide, lactic acid) and cobalt, chromium, nickel, platinum, tungsten, acrylic and fluoro polymers that cannot be adequately pre-medicated. Subject has a known contrast sensitivity that cannot be adequately pre-medicated.3. Subject has known allergic reaction, hypersensitivity or contraindication to any of the following: aspirin; or clopidogrel and prasugrel and ticagrelor; or heparin and bivalirudin, and therefore cannot be adequately treated with study medications.4. Subject had an acute STEMI (appropriate clinical syndrome with ≥ 1 mm of ST-segment elevation in ≥ 2 contiguous leads) within 72 hours of the index procedure.5. Subject has a cardiac arrhythmia identified at the time of screening for which at least one of the following criteria is met:⁴²
a. Subject requires coumadin or any other agent for chronic oral anticoagulation.b. Subject is likely to become hemodynamically unstable due to their arrhythmia.c. Subject has poor survival prognosis due to their arrhythmia.6. Subject has a left ventricular ejection fraction (LVEF) $< 30\%$ assessed by any quantitative method, including but not limited to echocardiography, MRI, multiple-gated acquisition (MUGA) scan, contrast left ventriculography, PET scan, etc. LVEF may be obtained within 6 months prior to the procedure for subjects with stable CAD. For subjects presenting with ACS, LVEF must be assessed within 1 week of the index procedure and after ACS presentation, which may include contrast left ventriculography during the index procedure but prior to randomization in order to confirm the subject's eligibility.

⁴² Investigator should use discretion when enrolling subjects with high CHADS scores.

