Periprocedural – patients with elevated baseline CK-MB in whom the biomarker levels have not been shown to be stable or falling as defined above (either because only one CK-MB was measured, or the most recent CK-MB measure in a series was either still increasing or had not decreased by	The CK-MB rises within 48 hours of the procedure by an absolute increment from the most recent CK-MB level of > 5 x ULN for post-PCI or > 10 x ULN for post-CABG plus new ST-segment elevation or depression plus signs consistent with a clinically relevant MI, such as new onset or worsening heart failure or sustained hypotension.	The following must also be present: 1. New ST-segment elevation or depression, 2. Plus signs consistent with a clinically relevant MI, such as new onset or worsening heart failure or sustained hypotension.

>25% from the most recent measure)		
Spontaneous (before or >48 hours after any coronary revascularization procedure)	Troponin >ULN or CK-MB > ULN	One or more of the following must also be present: - Symptoms of ischemia; - ECG changes indicative of new ischemia - (new ST-T changes or new LBBB), - Development of pathological Q waves; - Imaging evidence of a new loss of viable myocardium or a new regional wall motion abnormality

ULN=Upper limits of the local laboratory normal (will be collected from each hospital laboratory prior to study commencement); LBBB=Left Bundle-branch Block * Baseline CKMB value is required before study procedure and presumes a typical rise and fall post procedure to diagnose a peri procedure MI
 
** Whenever at least one baseline and one post procedure CK-MB measure are available in a patient with stable CAD, adjudication of MI will be based solely on these biomarker values. If the patient has stable ischemic heart disease and the baseline CK-MB measure are not available, they will be assumed to be within normal limits and MI will be adjudicated by the CEC solely according to the post procedure CK-MB measures. TROPONINS WILL NOT BE USED TO DIAGNOSE PERI-PROCEDURAL MI.
		

- **Periprocedural MI After PCI:**

The periprocedural period includes the first 48 hours after PCI.

- **Periprocedural MI After CABG:**

The periprocedural period includes the first 48 hours after coronary artery bypass grafting (CABG).

- **Spontaneous MI:**

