MI after the periprocedural period may be secondary to late stent complications or progression of native disease. Performance of ECG and angiography supports adjudication to either a target or non-target vessel in most cases.

With the unique issues and pathophysiological mechanisms associated with these later events as well as the documented adverse impact on short and long-term prognosis, a more sensitive definition than for periprocedural MI of any elevation of troponin or CKMB above the 99th percentile of the upper range limit (or ULN if URL is not available) is used. All late events that are not associated with a revascularization procedure will be considered simply as spontaneous.

Myocardial infarctions will also be adjudicated based on the following classification:

- **Q wave MI**

Development of new, pathological Q wave on the ECG (≥ 0.04 seconds in duration and ≥ 1 mm in depth) in ≥ 2 contiguous precordial leads or ≥ 2 adjacent limb leads)

- **Non-Q wave MI**

Those MIs which are not Q-wave MI.

Myocardial infarctions will also be adjudicated as to their relation to the Target Vessel

All infarcts that cannot be clearly attributed to a vessel other than the target vessel will be considered related to the target vessel.

For **Universal** and **WHO MI** definitions, please refer to ABSORB III protocol ([REDACTED], August 16, 2018). These definitions will be used for secondary analysis for ABSORB IV and ABSORB III.

ANGINA

Angina is defined as any angina or angina equivalent symptoms determined by the physician and/or research coordinator after interview of the patient, and as adjudicated by a clinical events committee (CEC).

ADVERSE EVENT [AE]

An adverse event (AE) is any untoward medical occurrence, unintended disease or injury, or untoward clinical signs (including abnormal laboratory findings) in subjects, users or other persons, whether or not related to the investigational medical device.

NOTE 1: This definition includes events related to the investigational medical device or the comparator.

NOTE 2: This definition includes events related to the procedures involved.

NOTE 3: For users or other persons, this definition is restricted to events related to investigational medical devices.

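### ABSORB IV takes over ABSORB III's WHO infarction definition without a baseline-enzyme condition, so a flat or falling enzyme curve from the enrolment infarct can be scored as a new peri-procedural MI in that secondary analysis

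*Protocol*

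**What the plan says.** **The imported rule.** ABSORB III Appendix II (modified WHO definition) scores a non-Q-wave MI when CK reaches at least two "times the upper limit of normal (ULN) with elevated CK-MB in the absence of new pathological Q waves". The next line extends it to the peri-procedural window: "Non-Q wave MI definition will be used for both peri-procedural MI definition" (up to 48 hours) and spontaneous MI. No normal baseline, increment or rise-and-fall is required. ABSORB IV Appendix II rewrites the protocol MI definition but leaves the Universal and WHO definitions as they stand in ABSORB III: "These definitions will be used for secondary analysis for ABSORB IV and ABSORB III".

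**Who could enter ABSORB III.** Section 6.3.1.2, exclusion 4, removes acute MI within 72 hours where "both CK and CK-MB have not returned to within normal limits at the time of index procedure". The footnote to Table 7.1 (section 7.2.1) adds, for acute or recent (under 7 days) MI or unstable angina, "in these cases CK and CK-MB must be < ULN prior to the index procedure". ABSORB III Appendix II labels a raised baseline CK-MB a protocol violation.

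**Who can enter ABSORB IV.** The ABSORB IV Protocol Summary, general inclusion criterion 3, admits "Unstable angina or NSTEMI within 2 weeks of the index procedure", and STEMI from 72 hours to 2 weeks before the procedure. General exclusion criterion 4 removes only STEMI within 72 hours. Neither sets a CK or CK-MB limit.

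**What ABSORB IV did adapt.** Its protocol MI table has rows for raised baseline enzymes, including "patients with elevated baseline CK-MB in whom the biomarker levels have not been shown to be stable or falling as defined above", and in those rows requires an increment over the most recent CK-MB.

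**The concern.** A fixed enzyme threshold works as a peri-procedural MI criterion only if patients start below it. ABSORB III's entry rules came close to guaranteeing that; ABSORB IV dropped them. Its authors plainly expected raised baselines, because they built them into the protocol MI table. The WHO definition did not receive the same treatment.

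At stake is whether the WHO analysis can be interpreted. If enrolment infarcts are counted as procedural ones, WHO MI rates are too high in both arms and the descriptive relative risks and hazard ratios (SAP 2.1.2 and 2.1.3) move towards 1. The same label also measures different things in ABSORB III and ABSORB IV. That matters because Appendix II uses it for both trials and SAP 2.1 and 2.2 plan summaries of the pooled 4600 subjects.

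**Working it through.** The plan states no figure on this point, so there is none to reproduce. The check applies the rules as written, then illustrates size under labelled assumptions.

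**1. The definitions side by side**

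| Definition | Baseline handling for peri-procedural MI |
|---|---|
| ABSORB IV protocol MI | Normal baseline, or CK-MB increment over 5x ULN (post-PCI); ECG and clinical signs as well if levels are not shown to be stable or falling |
| Universal | Normal baseline, or a rise over 20% if the baseline is raised and stable or falling |
| Modified WHO | None |

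**2. The rules applied to enzyme profiles with no new rise** (multiples of ULN, CK / CK-MB). WHO: post-procedure CK at least 2 and CK-MB above 1. Protocol: CK-MB increment above 5.

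| Before | After | WHO | Protocol |
|---|---|---|---|
| 3 / 3 | 3 / 3 | MI | no MI |
| 4 / 4 | 2.5 / 2.2 | MI | no MI |
| 1.6 / 1.5 | 1.6 / 1.5 | no MI | no MI |

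The draws that would show this are mandatory: 6–12 hours and 18–24 hours after the procedure (ABSORB IV 7.4.2). The third row marks the limit of the problem: CK must still be at least 2x ULN, with CK-MB raised, at a draw inside 48 hours.

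**3. How many subjects.** Assumptions, since the documents give neither input: 5–20% of subjects enter with recent NSTEMI or STEMI, and 10–40% of those are still above the WHO threshold at a post-procedure draw.

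- Low: 0.05 × 0.10 = 0.5%; 0.005 × 2600 = 13 subjects.
- High: 0.20 × 0.40 = 8%; 0.08 × 2600 = 208 subjects.

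**4. Effect on the comparison.** Let a be the carry-over share, equal in both arms by randomization. The observed rate is 1 − (1 − p)(1 − a), so the risk difference is multiplied by (1 − a). Illustrative true rates are 2.2% and 4.4%. The 2.2% is the 30-day MI rate quoted for ABSORB EXTEND (ABSORB III section 2.1.9), used for scale only because it is not stated to be a WHO rate; the 4.4% is assumed. The upper limit is difference + 1.96 × √[p₁(1 − p₁)/1300 + p₂(1 − p₂)/1300].

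| a | Rates | RR | Difference | Upper 95% limit |
|---|---|---|---|---|
| 0 | 2.20% v 4.40% | 2.00 | 2.20 points | 3.6 points |
| 2% | 4.16% v 6.31% | 1.52 | 2.16 points | 3.9 points |
| 5% | 7.09% v 9.18% | 1.29 | 2.09 points | 4.2 points |

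Rates and ratios move a lot. The risk difference barely moves, and its interval widens.

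**The case against.** The strongest reply is that no decision rests on this analysis. ABSORB IV Appendix II assigns the protocol MI definition, which handles raised baselines, to the primary analysis, and the TLF definitions in ABSORB IV 5.1 and 10.1 name it. Section 10.4.3 makes secondary endpoints other than the powered ones descriptive. This stands, and it limits how much the point matters.

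Four stronger readings are tempting, and the documents do not support them.

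- A reader might infer that the primary or powered TLF results are contaminated. They use the protocol definition.
- A reader might infer that diluted ratios make non-inferiority easier to claim. The trial tests risk differences by Farrington and Manning, with margins of 2.9% and 4.8% (SAP 1.5.1 and 1.5.2.1). On that scale the table above shows a nearly unchanged difference and a higher upper limit, so a WHO-based check would be harder to pass.
- A reader might infer that every enrolment infarct is miscounted. Only those still above the threshold at a draw within 48 hours can be.
- A reader might infer that a WHO-based TLF is planned. No visible text says so; Appendix II says only that MI will be adjudicated this way as a secondary analysis.

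It can also be said that the clinical events committee would use judgement. The committee's section (ABSORB III 9.1) and parts of the SAP are not visible, so a rule there cannot be excluded. The exclusion of unchanged or pre-existing conditions in ABSORB IV 8.3.1 governs adverse event reporting; it does not amend the WHO criterion.

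**Conclusion.** The point holds for the secondary WHO MI analysis. As written, the definition can score a flat or falling enzyme curve from the qualifying infarct as a new peri-procedural MI, in a trial that admits such patients. WHO MI rates would be inflated in both arms, descriptive relative risks and hazard ratios diluted, noise added to the risk difference, and comparability with ABSORB III lost. Randomization should balance the false events, so neither arm is directly favoured.

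The size cannot be determined from the documents. The range of 13 to 208 subjects rests entirely on the assumed shares above. The conclusion also assumes that no committee rule outside the visible text already supplies a baseline condition. It is worth correcting, but it does not threaten the main conclusions.

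**What to change.** In ABSORB IV Appendix II, restate the WHO definition for the first 48 hours only. When the last pre-procedure CK-MB, together with CK, is above ULN, a WHO non-Q-wave MI requires a new rise over that last value: a CK increment of at least 2x ULN with CK-MB also rising. This is the incremental principle already used in the protocol MI table. Under it the profiles above give increments of 3 − 3 = 0 and 2.5 − 4 = −1.5, so neither is an MI; a rise from 4 to 7 (increment 3) with CK-MB rising still is.

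Alternatively, leave the definition alone and report WHO MI in subjects with normal baseline CK and CK-MB alongside the full set.

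The index baseline increment should not be carried beyond 48 hours. A subject who entered at 4x ULN would then need 4 + 2 = 6x ULN at any later date, and a genuine late infarct peaking at 5x ULN would be missed. After 48 hours, at most require that enzymes have first normalised or show a new rise.

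The cost is one clause and a matching line in the adjudication rules. Pre-procedure, sheath and post-procedure CK and CK-MB are already collected (ABSORB IV Protocol Summary, Cardiac Biomarker Collection; sections 7.2.1 and 7.4.2), so no new data are needed.
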